### **3.6. Baseline Characterization**

Each analysis sample will be summarized overall and by treatment group for the following characteristics: randomization site; age, gender, race, and ethnicity; education level, years of education; years since PD diagnosis, years since PDD diagnosis, UPDRS Part I, II, III, I-III, IV A, IV B, and IV C total scores, and Hoehn and Yahr Stage; CDR COA, QEM, QWM, POA, and SWM composite scores; ADAS-cog total score; MoCA total score; PDAQ-15 total score; SAPS-PD total score; SCOPA-SLEEP nighttime sleep, overall sleep quality, and daytime sleepiness; NPI domain-specific and overall score and overall caregiver distress score; weight and body mass index; orthostasis and orthostatic changes in systolic and diastolic blood pressure; QTc interval by Fridericia's equation; baseline specific cholinesterase inhibitor; baseline memantine use, and baseline LDD and LEDD. The magnitude of differences between treatment groups will be summarized using Fisher's exact tests for nominal variables, exact Cochran-Armitage trend tests for ordinal variables, and two-sample t-tests for approximately continuous variables.

### **3.7. Interim Analysis**

No interim analysis for futility, efficacy, or sample size re-estimation is planned. The independent Safety Data Monitor and the Safety Data Monitor Advisory Group review safety data quarterly and may request specific analyses at any time.

## 3.8. Efficacy Analysis

### 3.8.1. Primary Analysis of the Primary Efficacy Endpoint

The primary efficacy analysis will be performed on the mITT sample using the adjudicated CDR data and will use a shared-baseline, repeated-measures analysis of variance that includes fixed effects for visit (3 levels: Baseline, Week 8, and Week 16) and the interaction between treatment group (2 levels: SYN120 and placebo) and post-baseline visit (2 levels: Weeks 8 and 16), random center-specific intercepts, and unstructured within-person covariance. The interaction between treatment group and visit will be restricted to post-baseline visits by including a numeric indicator variable (0 pre-treatment, 1 post-treatment) in the interaction. Use of a shared baseline reflects the true state of the population sampled prior to randomization and has the advantage of adjusting for any chance differences at baseline in a manner similar to analysis of covariance ([Liang and Zeger, 2000](#)) with potentially greater efficiency with more than one follow-up visit and drop-out. Data from Early Termination visits will be assigned to the next scheduled post-baseline visit. The following SAS code specifies the model:

```
proc mixed data=xxx method=reml;
  class site id trtrnd visit;
  model Value = visit post*trtrnd*visit;
  random intercept / subject=site type=vc;
  repeated visit / subject=id(site) type=un;
```

Treatment-dependent differences in the change from baseline to the week 16 visit on the CDR COA will be estimated by a linear contrast and tested using a two-tailed Wald-test at alpha = 0.05. The following SAS code specifies the linear contrasts used to estimate treatment- and visit-specific means, treatment- and visit-specific changes from baseline, and treatment-dependent visit-specific changes from baseline (with the sort order for treatment group being SYN120 first and placebo second):

```
estimate "0|Active |Wk  00" intercept 1 visit  1 0 0 post*trtrnd*visit 0 0 0  0 0 0 / cl;
estimate "0|Active |Wk  08" intercept 1 visit  0 1 0 post*trtrnd*visit 0 1 0  0 0 0 / cl;
estimate "0|Active |Wk  16" intercept 1 visit  0 0 1 post*trtrnd*visit 0 0 1  0 0 0 / cl;
estimate "1|Active |dWk 08" intercept 0 visit -1 1 0 post*trtrnd*visit 0 1 0  0 0 0 / cl;
estimate "1|Active |dWk 16" intercept 0 visit -1 0 1 post*trtrnd*visit 0 0 1  0 0 0 / cl;
estimate "0|Placebo|Wk  00" intercept 1 visit  1 0 0 post*trtrnd*visit 0 0 0  0 0 0 / cl;
estimate "0|Placebo|Wk  08" intercept 1 visit  0 1 0 post*trtrnd*visit 0 0 0  0 1 0 / cl;
estimate "0|Placebo|Wk  16" intercept 1 visit  0 0 1 post*trtrnd*visit 0 0 0  0 0 1 / cl;
estimate "1|Placebo|dWk 08" intercept 0 visit -1 1 0 post*trtrnd*visit 0 0 0  0 1 0 / cl;
estimate "1|Placebo|dWk 16" intercept 0 visit -1 0 1 post*trtrnd*visit 0 0 0  0 0 1 / cl;
estimate "2|ActvPlb|dWk 08" intercept 0 visit  0 0 0 post*trtrnd*visit 0 1 0  0 -1 0 / cl;
estimate "2|ActvPlb|dWk 16" intercept 0 visit  0 0 0 post*trtrnd*visit 0 0 1  0 0 -1 / cl;
```

The estimate labeled "2|ActvPlb|dWk 16" specifies the primary hypothesis. A significant mean improvement over 16 weeks in CDR COA among participants randomized to SYN120 relative to mean changes among participants randomized to placebo would be considered evidence of therapeutic benefit from SYN120.

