10.8 Determination of Sample Size

A total sample size of 80 or 40 in each group will provide at least 80% power to detect a true treatment difference equal to an effect size of 0.69 assuming up to 15% loss to follow up and using a two-tailed test at alpha = 0.05 based on a simple two-sample t-test. Additional power will be obtained from the proposed analysis using a shared-baseline repeated measures ANOVA.

Approximately 120 patients will be screened, assuming a 33% screen failure rate, to randomize 80 patients.

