### **3.8.5. Multiplicity Adjustments**

A single primary efficacy outcome is specified with a single treatment comparison and a pre-specified primary analysis with no interim analysis. Therefore, no multiplicity exists for the primary analysis, and inference will be based on two-tailed testing at alpha = 0.05. If the primary analysis is significant, then testing the key secondary outcome at alpha = 0.05 maintains an overall type I error rate at 5% under a closed testing sequential analysis. When the primary analysis is not significant, we limit the overall type I error rate to 10% or less (depending on the magnitude of correlation between the primary and key secondary outcomes) when significance of the key secondary outcome alone is accepted as evidence of a therapeutic benefit from SYN120. Results from analysis of non-key secondary efficacy endpoints, exploratory efficacy endpoints, and subgroup analyses will report nominal, comparison-wise p-values, recognizing that the totality of results will be evaluated in judging the potential of SYN120 as a therapeutic agent for PDD.

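### The primary Wald test carries no small-sample correction, so at this trial's size it rejects slightly too often (about 5.4% to 5.7% instead of 5%)

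*SAP*

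**What the plan says.** SAP 3.8.1 prints the primary model in full. The call is "proc mixed data=xxx method=reml", the fixed part is "model Value = visit post*trtrnd*visit", and the two covariance statements are "random intercept / subject=site type=vc" and "repeated visit / subject=id(site) type=un". Nothing follows the MODEL statement, so no denominator-df method is chosen. The Week 16 difference is "estimated by a linear contrast and tested using a two-tailed Wald-test at alpha = 0.05". Protocol 10.4.1 also names only a Wald test. Neither document mentions Kenward-Roger, Satterthwaite or any other adjustment.

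SAP 3.8.5 treats this as the one primary test and says that "inference will be based on two-tailed testing at alpha = 0.05". On size, Protocol 10.8 states: "A total sample size of 80 or 40 in each group will provide at least 80% power". That figure is for an effect size of 0.69 with up to 15% loss, and it is based on a two-sample t-test.

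The model is reused for the key secondary, other secondary and exploratory endpoints (SAP 3.8.3) and for the UPDRS safety scores (SAP 3.9.6).

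**The concern.** Two things make a plain Wald test optimistic in a trial this small.

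- **Standard error.** The model-based standard error treats the covariance matrix as known. Here seven parameters are estimated: six in the unstructured 3x3 matrix and one site variance. On average the reported standard error is therefore a little too small.
- **Reference distribution.** A treatment difference is a between-patient contrast, and its information is governed by the number of patients. A normal reference, or degrees of freedom counted from individual observations, claims more.

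Both errors act in the same direction: intervals too narrow and p-values too small. This is the test on which the primary claim rests. SAP 3.8.5 also limits the overall type I error to 10% when the key secondary outcome alone is accepted as evidence, and that limit assumes that each test holds 5%. Finally, SAP 3.1.1 allows either SAS or R, so with no df method named, a borderline p-value could depend on the software used.

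**Working it through.** **Inputs from the documents.** 80 randomized, 40 per arm, up to 15% loss, effect size 0.69, two-sided 0.05 (Protocol 10.8); permuted blocks of 4 by site (SAP 2.5); 20 sites (SAP 2.3) or approximately 12 (Protocol 3.1.2); the model and contrast of SAP 3.8.1.

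**Assumed, because the documents give no values.** Within-person correlation 0.3 to 0.8; site variance 0 to 0.1 relative to a within-site variance of 1; timing of dropout; normal data.

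**1. The plan's own figure.** 40 × 0.85 = 34 per arm. A two-sample t-test with 34 per arm and d = 0.69 has noncentral-t power of 80.05%, and 68/0.85 = 80. The stated 80% is reproduced. That calculation uses 34 + 34 − 2 = 66 degrees of freedom.

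**2. Degrees of freedom in the code as printed.** The PROC MIXED default here is the containment method, N − rank[X Z]. With 34 complete patients per arm there are 68 × 3 = 204 observations. X has rank 5 (three visits, two interaction terms) and 20 sites add 19, so df = 204 − 24 = 180. Across the scenarios below it runs from 180 to 204. The Kenward-Roger run gave a median of about 65 to 67.

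**3. Effect of the df alone.** If the statistic truly has 66 df:

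- z critical value: 2·P(t66 > 1.960) = 0.0542
- critical value from about 190 df: 2·P(t66 > t0.975,190) = 0.0527

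So the df error alone explains only part of the excess.

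**4. Simulation of the full model.** 20,000 null trials per scenario, Monte Carlo SE about 0.0016:

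| Scenario | z | t, default df | Kenward-Roger |
|---|---|---|---|
| 20 sites, 34 per arm complete | 0.0556 | 0.0541 | 0.0482 |
| 20 sites, 7.5% lost before Week 8, 15% by Week 16 | 0.0566 | 0.0552 | 0.0482 |
| 20 sites, 15% missing at Week 16 only | 0.0572 | 0.0556 | 0.0489 |
| 12 sites, 7.5% / 15% | 0.0588 | 0.0571 | 0.0519 |
| 20 sites, 7.5% / 15%, correlation 0.3, no site variance | 0.0574 | 0.0560 | 0.0498 |
| 20 sites, 7.5% / 15%, correlation 0.8, site variance 0.1 | 0.0563 | 0.0548 | 0.0482 |

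The first four rows use correlation 0.6 and site variance 0.05. The Monte Carlo SE at exactly 5% is √(0.05 × 0.95 / 20,000) = 0.00154. The default-df column lies 2.7 to 4.6 of these above 0.05; Kenward-Roger stays within about 1.2.

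**5. Standard error and interval width** (34 per arm complete). The mean model SE is 0.1919, the empirical SD 0.1959 and the Kenward-Roger SE 0.1951. The model SE is 0.1919/0.1959 = 0.980 of the truth, or 2% low; across scenarios the shortfall is 2% to 3%.

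- Half-width as printed: 1.973 × 0.1919 = 0.3786
- Half-width with Kenward-Roger: 1.997 × 0.1951 = 0.3896
- Ratio: 0.972, so about 3% too narrow

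An uncorrected p of exactly 0.05 corresponds to a Kenward-Roger statistic of 1.973 × 0.1919/0.1951 = 1.941, that is p of about 0.057.

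**6. The 10% limit in SAP 3.8.5.** Assume both endpoints share the same error rate and are independent. Two tests at 5% give 1 − 0.95² = 9.75%. At 5.41% they give 1 − 0.9459² = 10.5%, and at 5.71%, 1 − 0.9429² = 11.1%. Positive correlation between the endpoints lowers these figures.

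**The case against.** The strongest counter-argument is size. This is a phase 2a study whose SAP openly accepts up to 10% overall error when the key secondary alone is positive, and reports nominal p-values for everything beyond it. Half a percentage point is small beside that. This stands as an argument about priority, but it does not make the test correct.

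Other points have partial force:

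- **SAS prints a t-test, not z.** True, but the default-df t-test still rejects in 5.4% to 5.7% of null trials and leaves the standard error uncorrected.
- **A small simulation cannot show this.** Also true. A run of 4,160 trials gave 5.5% (z), 5.3% (default-type df) and 4.8% (Kenward-Roger), with a Monte Carlo SE of 0.35%, which does not separate 5.3% from 5%. The 20,000-trial runs do.
- **34 per arm is a planning limit.** The mITT set needs only one post-baseline score, and patients who stop drug stay in follow-up, so it may be larger. With 40 per arm and complete data, a separate check of 200,000 trials per setting (no site variance) still gave 5.3% to 5.4% with default df.
- **Kenward-Roger is not the truth.** Measured against the empirical SD instead, the interval is 0.3786/(1.997 × 0.1959) = 0.968 of the required width, so the shortfall does not shrink.
- **Other analyses avoid this standard error.** The site-stratified rank analyses in SAP 3.8.2 do, but they are secondary and do not repair the primary test.
- **Nothing was computed for the random-slopes model.** Correct. Extending the option to it rests on consistency.

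**Conclusion.** The concern holds. Followed exactly, SAP 3.8.1 gives a slightly liberal primary test: about 5.4% to 5.7% with the printed code and 5.6% to 5.9% with a z reference, against a nominal 5%. Intervals are about 3% too narrow. Kenward-Roger brings the rate to 4.8% to 5.2%. With 34 per arm, complete data and no site variance, the separate check gave 5.5% with about 190 df and 5.6% to 5.7% with z, against 5.0% to 5.1% for an exact between-patient t-test.

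The exact figures depend on the assumed correlation, site variance, dropout timing and normality, but the direction was the same in every scenario, with 12 or 20 sites. The effect matters only for a borderline result. It should still be corrected before unblinding, because the error favours the drug and the remedy is trivial.

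**What to change.** In SAP 3.8.1, extend the statement "model Value = visit post*trtrnd*visit" with `/ ddfm=kr`, and say in the text that all contrasts are t-tests with Kenward-Roger standard errors and degrees of freedom, whichever software is used. Make the same addition to the random-slopes code in SAP 3.8.2 so that the primary and sensitivity models are treated alike. Endpoints that refer back to 3.8.1 then inherit the method. SAP section 1 makes the SAP authoritative on analysis, so changing it there is sufficient.

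The cost is one model option and one sentence, with no new data or patients. P-values become very slightly larger. The stated power is not undermined: its basis is a t-test with 66 df, close to the 65 to 67 that Kenward-Roger gives.

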### 3.8.2. Secondary Analyses of the Primary Efficacy Endpoint

Several secondary analyses will be investigated to assess sensitivity of our estimates of treatment effect to alternative modeling assumptions and alternative handling of the CDR data.

- Random-slopes model: The repeated-measures covariance will be replaced with random participant-level intercepts and slopes with unstructured covariance. Data from Early Termination visits will be placed at their observed follow-up time. The following SAS code

specifies the model and the linear contrasts used to estimate treatment-specific and treatment-dependent changes over 16 weeks:

```
proc mixed data=xxx method=reml;
  class site id trtrnd;
  model Value = week trtrnd*week;
  random intercept / subject=site type=vc;
  random intercept week / subject=id(site) type=un;
  estimate "1|Active |Chg 16" intercept 0 week 16 trtrnd*week 16 0 / cl;
  estimate "1|Placebo|Chg 16" intercept 0 week 16 trtrnd*week 0 16 / cl;
  estimate "2|ActvPbl|Chg 16" intercept 0 week 0 trtrnd*week 16 -16 / cl;
```

- Shared-baseline, repeated-measures ANOVA model with pMI for missing data: The shared-baseline repeated-measures ANOVA model described above for the primary analysis will be applied to datasets generated by placebo multiple imputation (Ayele et al. 2014). Fifty imputed datasets will be generated for a given endpoint.
- Cochran-Mantel-Haenszel row mean score LOCF: 16-week change scores will be compared by mean score test using modified ridit scores stratified by clinical site. The last observed CDR COA value will be carried forward when CDR COA values are not available from the Week 16 visit. The following SAS code specifies the model:

```
proc freq data=xxx;
  table site * trtrnd* Value / cmh scores=modridit;
```

- Cochran-Mantel-Haenszel row mean score WO: 16-week change scores will be compared by mean score test using modified ridit scores stratified by clinical site. The worst observed CDR COA 16-week change from baseline will be imputed when CDR COA values are not available from the Week 16 visit.
- PP sample: The primary efficacy model and the secondary random-slopes model will be applied to the PP sample.
- Alternative CDR data: The primary efficacy model and the secondary random-slopes model will be applied to mITT and PP samples using the raw CDR data.

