### **2.3. Study Population**

Individuals eligible for trial participation are men or women at least 50 years old who have received a diagnosis of probable PDD according to the Movement Disorder Society Task Force clinical diagnostic criteria for dementia associated with Parkinson's disease ([Emre et al. 2007](#)) and who are taking a cholinesterase inhibitor. Detailed inclusion and exclusion criteria are specified in the clinical protocol.

Participants will be recruited from a total of 20 clinical sites located through the US.

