## 3.3. Measurement Definitions

### 3.3.1. CDR Measures

The CDR ([Wesnes et al. 1992](#)) is a computerized neuropsychological test battery to assess cognitive tasks based on measures of choice reaction time, vigilance, and the sensitivity and speed of digit, word and picture recognition. The stimuli are presented on a computer screen and the subjects respond by pressing either a “Yes” or “No” on a response box. Detailed of the assessments are described in the clinical protocol.

Continuity of Attention (COA) measures the ability to sustain attention and avoid error. COA is calculated as  $(VIGACC*0.45) + (CRTACC*0.5) - VIGFA$ , where VIGACC is digit vigilance accuracy, CRTACC is choice reaction time accuracy, and VIGFA is digit vigilance false alarms. Higher COA scores represent greater sustained attention and avoidance of errors.

Quality of Episodic Memory (QEM) measures the ability to store, hold, and retrieve information of an episodic nature. QEM is calculated as  $(DRECOACC + DRECNACC - 100) + (DPICOACC + DPICNACC - 100) + ((IRCL - IRCLERR)*100 / 12) + ((DRCL - DRCLERR)*100 / 12)$ , where DRECOACC is word recognition original stimuli accuracy, DRECNACC is word recognition new stimuli accuracy, DPICOACC is picture recognition original stimuli accuracy, DPICNACC is picture recognition new stimuli accuracy, IRCL is immediate word recall words recalled, IRCLERR is immediate word recall errors, DRCL is delayed word recall words recalled, and DRCLERR is delayed word recall errors. Higher QEM scores represent greater ability to store, hold, and retrieve information of an episodic nature.

Quality of Working Memory (QWM) measures the ability to store and retrieve information in working memory. QWM is calculated as SPMSI + NWMSI, where SPMSI is the sensitivity index for spatial working memory and NWMSI is the sensitivity index for numeric working memory. Sensitivity index ([Frey and Collier 1973](#)) measures the ability to identify previously presented stimuli and reject stimuli which were not previously presented. A score of 1 represents perfect discrimination; all of the previously presented stimuli are correctly identified and all distractor stimuli are correctly rejected as being novel. A score of -1 represents perfect reverse discrimination; none of the previously presented stimuli are correctly identified, and all distractor stimuli are selected as being novel. A score of 0 represents chance performance with no

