### 3.4. Determination of Sample Size

The primary efficacy measure is the change from baseline to the week 16 visit in the CDR COA. Based on a two-tailed test at alpha = 0.05 and assuming up to 15% loss to follow up, a total sample size of 80 randomized participants provides at least 80% power for a true treatment-dependent difference in 16-week change in CDR COA equal to an effect size of 0.69. Additional power will be obtained from analysis using a shared-baseline repeated-measures analysis of

variance. Effect sizes of similar magnitude were observed for several CDR measures in a 24-week trial of memantine in patients with PDD and dementia with Lewy bodies ([Wesnes et al. 2014](#)).

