### **3.8.6. Missing Data**

Baseline values for efficacy endpoints will be determined from the last non-missing data collected prior to the first dose of study medication. The planned repeated-measures model yields estimates that are unbiased conditional on the observed scores under a missing at random assumption. In addition, a secondary analysis of the primary endpoint will use placebo-based multiple imputation of missing data. The Cochran-Mantel-Haenszel row mean score LOCF and WO analyses provide estimates of treatment effect when normality assumptions are violated. Additional sensitivity analyses may be pursued to impute missing values or otherwise construct models for unobserved outcomes if more than 20% of participants are missing follow-up data for any reason.

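### The SAP's only non-normality checks on COA rank unadjusted change within sites of about 4 patients and give a p-value, not the estimate that Section 3.8.6 promises

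*SAP*

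**What the plan says.** The primary analysis (SAP 3.8.1) is a shared-baseline, normal-theory mixed model. The SAP commends it for adjusting for chance baseline differences.

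Among the secondary analyses in SAP 3.8.2, two are rank-based, and both carry the sentence "16-week change scores will be compared by mean score test using modified ridit scores stratified by clinical site". One carries the last COA value forward. The other imputes the worst observed 16-week change. The SAS call is a frequency procedure on site by treatment by value, with CMH statistics and modified ridit scores. It has no baseline term and names no estimator.

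SAP 3.8.6 gives these analyses their role: "The Cochran-Mantel-Haenszel row mean score LOCF and WO analyses provide estimates of treatment effect when normality assumptions are violated".

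Three other statements matter:
- Sites (SAP 2.3): "Participants will be recruited from a total of 20 clinical sites located through the US". Protocol 3.1.2 gives about 12.
- The COA formula (SAP 3.3.1; the opening bracket is outside the quote): "VIGACC*0.45) + (CRTACC*0.5) - VIGFA".
- Sample size (SAP 3.4): "a total sample size of 80 randomized participants" and an effect "equal to an effect size of 0.69".

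SAP 3.8.3 applies the same set of models to the key secondary endpoint, Quality of Episodic Memory.

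**The concern.** COA has a fixed upper limit and false alarms only lower it, so left skew is plausible and the rank analyses may be needed. The other analyses in SAP 3.8.2 (random slopes, placebo-based imputation, per-protocol sample, raw CDR data) are normal-theory mixed models. The log-transformation rule in SAP 3.8.3 covers strictly positive, right-skewed variables and does not name COA.

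The planned tests give up information in two ways. Ranking inside very small strata leaves little contrast per site, and a site left with one arm contributes nothing. Using change scores forgoes the baseline adjustment that the primary model has.

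At stake is how a robustness result is read. A real effect of the design size could look fragile because the check is weak, and there would be no non-parametric estimate to set beside the p-value.

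**Working it through.** **1. The plan's own figure.** SAP 3.4 states "Based on a two-tailed test at alpha = 0.05 and assuming up to 15% loss to follow up" and "provides at least 80% power for a true treatment-dependent" difference of effect size 0.69; Protocol 10.8 names a two-sample t-test. Evaluable patients: 80 × 0.85 = 68, or 34 per arm. Noncentrality: 0.69 × √(34/2) = 2.845 on 66 degrees of freedom. Power is 80.05%, so the stated figure reproduces. With all 40 per arm it is 86.2%.

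**2. Stratum size and ceiling.** 80/20 = 4 patients per site (80/12 ≈ 6.7 at the protocol's count). Maximum COA = 0.45 × 100 + 0.5 × 100 − 0 = 95.

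**3. Where power goes.** The following simulation used normal data, 20 sites of 4 with blocks of 4 (SAP 2.5), no site effect on change, effect 0.69 on change and an assumed correlation of 0.6. Missing values were deleted, which is not the planned handling. Power in %:

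| Values present | t-test on change | Unstratified rank test on change | Site-stratified CMH | ANCOVA | Unstratified rank ANCOVA |
|---|---|---|---|---|---|
| 80 | 85.8 | 84.2 | 74.8 | 92.4 | 89.9 |
| 68 | 80.0 | 77.8 | 64.5 | 87.1 | 84.2 |

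At 80 values, stratifying the rank test costs 84.2 − 74.8 = 9.4 points. Forgoing baseline adjustment costs 92.4 − 85.8 = 6.6 points on the parametric scale.

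**4. The tests as planned.** With 12 missing Week 16 values imputed (correlation 0.6, all 12 having a Week 8 value), the LOCF version has 67% power if half the effect is present at Week 8 and 75% if all of it is. The worst-outcome version has about 48-49%.

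**5. Against a site-stratified rank ANCOVA.** This comparison used LOCF, 20 sites of 4, full effect by Week 8, correlation 0.5 to 0.8, and rank-ANCOVA residuals used directly as scores:

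| Assumed data | Planned CMH | Rank ANCOVA |
|---|---|---|
| Normal | 70-75% | 82-91% |
| Strong left skew, capped | 53-59% | 83-92% |

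Type I error was about 4-6% for both.

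**6. Sensitivity to shape.** Absolute power under non-normality depends heavily on the assumed shape. The runs here used complete cases at 20 sites of 4. For a simulated COA-like score with a ceiling at 95, CMH had 85.0% (80 values) and 71.9% (68), against 98.0% and 95.4% for an unstratified rank ANCOVA. Under a different left-skewed model, CMH had 92-98% and beat the t-test on change by about 10-12 points. With heavy tails (t, 3 df) the two were about equal: 87.0 against 86.0 at 80 values, and 79.9 against 82.3 at 68.

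**7. Estimate or test.** SAP 3.8.6 promises estimates. The call in SAP 3.8.2 yields a row-mean-score statistic and p-value, and no shift, win probability or interval is specified anywhere for these analyses. This needs no simulation.

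**The case against.** These are sensitivity analyses. The primary inference rests on a model that already uses baseline, and nothing in the SAP makes the CMH result a gate. Stratifying by site matches the randomization, type I error is sound, and Protocol 10.4.1 plans a van Elteren test of the same kind. All of that stands. It limits the importance of the point but does not remove it.

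A reader might infer more than the documents support:
- **A general loss of 12-17 power points.** That range belongs to normal data, a t-test comparator and 20 sites. At 12 sites the loss is about 8-12 points, and under some skewed shapes the CMH test beats the t-test.
- **Power of 63-68% for the planned test.** That is a complete-case figure. The SAP imputes missing Week 16 values, which refills most strata.
- **The CMH tests replace the primary analysis if normality fails.** No text says so.
- **Any rank ANCOVA recovers the power.** If residuals are re-ranked within site by modified ridits, aligning them first changes nothing. In one set of LOCF runs that version gave 80% against 75% at correlation 0.6, but 72% against 74% at 0.8. Ranking Week 16 COA instead of change also does not fit the SAP's worst-change rule and can lose power there.

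**Conclusion.** The point holds as a recommended improvement to a sensitivity analysis. Two parts rest on the documents alone: the SAP's non-normality checks on COA are all of one kind, without baseline adjustment beyond subtraction, and 3.8.6 promises estimates that the specified code cannot give.

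The size rests on assumptions: effect size 0.69, 20 sites of 4, correlation 0.5 to 0.8, full effect by Week 8 and no site effect on change. On those, the planned LOCF test has about 70-75% power with normal data and about 53-59% under one strong capped skew, against about 82-92% for the baseline-adjusted version. The skewed figures are illustrative, since other plausible shapes give much higher CMH power. The gain shrinks as the correlation rises and is smaller for the worst-outcome version. The primary analysis is not affected. The same structure carries over to Quality of Episodic Memory, for which no power was computed.

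**What to change.** Before unblinding, amend SAP 3.8.2 for both imputations:
1. Form the 16-week change with the LOCF or worst-change rule as now written.
2. Rank the change across all patients and regress it on ranked baseline COA.
3. Use the residuals directly as scores in the site-stratified mean-score test, without re-ranking within site.

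Report a Hodges-Lehmann shift in change with a 95% CI, stating whether it is stratified by site. If it is not derived from the adjusted test, say so, because interval and p-value may then disagree. Otherwise, delete the statement in SAP 3.8.6 that these analyses provide estimates. Carry the same change to the key secondary endpoint.

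The cost is a few lines of code. No new data are needed, and site stratification is kept.
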